7.2.5 Final Study Visit (Day 14-16) (may be remote)*

- AHRS and DESA
- SAFTEE & addendum
- C-SSRS
- BPRS

7.2.6 Withdrawal/Early Termination Visit*

If a participant withdraws or terminates early, the following assessments will be completed:

- AHRS and DESA
- SAFTEE & addendum

- C-SSRS
- BPRS

*All remote visits will take place over WebEx, a secure video conferencing platform.

7.3 Concomitant Medications, Treatments, and Procedures

All concomitant medications will be allowed with the exception of anticonvulsants (including benzodiazepines). Concomitant prescription medications taken during study participation will be recorded on the case report forms (CRFs). For this protocol, a prescription medication is defined as a medication that can be prescribed only by a properly authorized/licensed clinician. Medications to be reported in the CRF are concomitant prescription medications, over-the-counter medications and non-prescription medications.

7.4 Justification for Sensitive Procedures

A sham sonication procedure will be included so that results are interpretable. Without a sham control, results are of very poor validity and the contribution of participants to the development of the science is compromised. Because we are employing a cross-over design, all participants will receive active PLIFUS.

7.4.1 Precautionary Medications, Treatments, and Procedures

7.5 Prohibited Medications, Treatments, and Procedures

Anticonvulsants, including benzodiazepines will be prohibited because they affect neuronal excitability and may mask the effect of PLIFUS.

7.6 Prophylactic Medications, Treatments, and Procedures

7.7 Rescue Medications, Treatments, and Procedures

We do not anticipate that rescue medication will be required.

7.8 Participant Access to Study Agent at Study Closure

PLIFUS is not currently available as a clinical procedure.

7.9 Assessment of Safety

7.10 Specification of Safety Parameters

Safety will be assessed by close monitoring by a study psychiatrist during and for 1 hour after each sonication/sham session by assessment of psychiatric symptoms and side effects (SAFTEE & addendum). SAFTEE, SAFTEE addendum, and CSSRS will be repeated one day and one week after each session. The difference between post-sonication and post-sham safety measures will be assessed for safety. In addition to serious adverse events that will be reported immediately, these data will be provided to the DSMB after the first 8 completers. If the dose is increased to 3 sessions, safety data will be provided to the DSMB after the 4 completers at the higher dose.

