7.2.4 Intervention Visits

Intervention Visit 1: (Day 0)

- Administer CGI, C-SSRS, SAFTEE, SAFTEE addendum, and PSYRATS
- Obtain structural MRI scan for fMRI registration (5 minutes)
- Obtain fMRI resting state scan (20 minutes)
- Administer AHRS and DESA prior to starting intervention
- Administer PLIFUS/sham over 10 minutes (re-administer AHRS and DESA at 5 minutes)
- Repeat AHRS and DESA immediately after PLIFUS/sham
- Obtain structural MRI scan for fMRI registration (5 minutes)
- Obtain fMRI resting state scan (20 minutes)
- AHRS and DESA repeated immediately after fMRI scan
- PSYRATS and CGI 60 minutes after PLIFUS/sham
- Psychiatric and medical assessment, including MoCA, SAFTEE, and SAFTEE addendum, 1 hour after PLIFUS/sham

Intervention Visit 1B: (Day 1-2) (may be remote)*

- AHRS and DESA
- SAFTEE & addendum
- C-SSRS

Intervention Visit 2 (Day 6-8)

- Administer CGI, C-SSRS, SAFTEE, SAFTEE addendum, and PSYRATS
- Obtain structural MRI scan for fMRI registration (5 minutes)
- Obtain fMRI resting state scan (20 minutes)
- Administer AHRS and DESA prior to starting intervention
- Administer PLIFUS/sham over 10 minutes (re-administer AHRS and DESA at 5 minutes)
- Repeat AHRS and DESA immediately after PLIFUS/sham
- Obtain structural MRI scan for fMRI registration (5 minutes)
- Obtain fMRI resting state scan (20 minutes)
- AHRS and DESA repeated immediately after fMRI scan
- PSYRATS and CGI 60 minutes after PLIFUS/sham
- Psychiatric and medical assessment, including MoCA, SAFTEE, and SAFTEE addendum, 1 hour after PLIFUS/sham

Intervention Visit 2B (Day 7-9) (may be remote)*:

- AHRS and DESA
- SAFTEE & addendum
- C-SSRS

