7.10.1 Definition of Adverse Events (AE)

An **adverse event** (AE) is any symptom, sign, illness or experience that develops or worsens in severity during the course of the study. Intercurrent illnesses or injuries should be regarded as adverse events. Abnormal results of diagnostic procedures are considered to be adverse events if the abnormality:

- results in study withdrawal
- is associated with a serious adverse event
- is associated with clinical signs or symptoms
- leads to additional treatment or to further diagnostic tests
- is considered by the investigator to be of clinical significance

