7.12 Time Period and Frequency for Event Assessment and Follow-Up

The occurrence of an AE or SAE may come to the attention of study personnel during study visits and interviews of a study participant presenting for medical care, or upon review by a study monitor. All AEs including local and systemic reactions not meeting the criteria for SAEs will be captured on the appropriate CRF. Information to be collected includes event description, time of onset, clinician's assessment of severity, relationship to study product (assessed only by those with the training and authority to make a diagnosis), and time of resolution/stabilization of the event. All AEs occurring while on study must be documented appropriately regardless of relationship. All AEs will be followed to adequate resolution.

Any medical condition that is present at the time that the participant is screened will be considered as baseline and not reported as an AE. However, if the study participant's condition deteriorates at any time during the study, it will be recorded as an AE. UPs will be recorded in the data collection system throughout the study.

Changes in the severity of an AE will be documented to allow an assessment of the duration of the event at each level of severity to be performed. AEs characterized as intermittent require documentation of onset and duration of each episode.

The PI will record all reportable events with start dates occurring any time after informed consent is obtained until 7 (for non-serious AEs) or 30 days (for SAEs) after the last day of study participation. At each study visit, the investigator will inquire about the occurrence of AE/SAEs since the last visit. Events will be followed for outcome information until resolution or stabilization.

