A study psychiatrist will be present during all sessions of PLIFUS and sham. Participants will be monitored during and after sonication until psychiatrically cleared by the study psychiatrist 1 hour after completion of each session. Participants will be contacted 24-48 hours and 7 days after each treatment period and symptoms, side effects and suicidality assessed.

9 Statistical Considerations

This is a pilot study intended to obtain preliminary data to guide future studies. The analysis will primarily be descriptive for this purpose and, due to the small sample size, effect sizes will be the primary signal of target engagement. Consistent with other studies in the field, we have selected an effect size of 0.5 as our threshold. In addition, there is a pre-planned review of results after completion of the first 5 participants; the administration of PLIFUS/sham will be increased from one session to three sessions over 5 days if an effect size of 0.5 or greater with PLIFUS is not detected in change from baseline in GPi functional connectivity or symptom response compared to sham.

The primary statistical analysis will be performed in completers without imputation of missing data and will be change in primary outcomes (GPi functional connectivity and symptom severity) from baseline to the first measure post-sonication or sham (immediately post-sonication for symptoms; 10-30 minutes for fMRI). PLIFUS and sham PLIFUS will be compared using a linear mixed effects model with baseline measures (GPI functional connectivity and severity of psychotic symptoms) as continuous variables; treatment (PLIFUS or sham) and sequence as categorical variables; and participant as a random effect. Similar secondary exploratory analyses will be performed at additional time points (symptom severity during sonication, 60 minutes, 1 day and 7 days after sonication). Secondary analyses of other outcome measures (BPRS total score, PSYRATS and CGI) will be analyzed following the same approach. Safety measures, including the SAFTEE and C-SSRS will be summarized descriptively. If the study design is adapted (sonication increased to 3 sessions) after the first 12 completers with good quality imaging data, results from the first 12 completers and subsequent 4 participants will be analyzed separately.

Sample Size

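### The safety contrast in Section 7.10 ignores the pre-session ratings, so a PLIFUS-induced symptom lasting to Visit 2 shrinks the PLIFUS-sham difference

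*Combined protocol and SAP*

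**What the plan says.** - Section 7.10 gives the comparison: "The difference between post-sonication and post-sham safety measures will be assessed for safety". It also sets later readings: "SAFTEE, SAFTEE addendum, and CSSRS will be repeated one day and one week after each session".
- Section 7.2.4 opens both intervention visits, before treatment, with: "Administer CGI, C-SSRS, SAFTEE, SAFTEE addendum, and PSYRATS". Each visit ends with: "Psychiatric and medical assessment, including MoCA, SAFTEE, and SAFTEE addendum, 1 hour after PLIFUS/sham". C-SSRS is not listed at 1 hour; it returns at the Day 1-2 and Day 7-9 contacts and at the final visit.
- After session 1, the one-week SAFTEE can only be the Visit 2 pre-session rating (Day 6-8). No other SAFTEE is scheduled then.
- Section 9 adds only: "Safety measures, including the SAFTEE and C-SSRS will be summarized descriptively". No SAFTEE score or change rule is defined.
- Section 7.12 names a baseline, for adverse event reporting: "Any medical condition that is present at the time that the participant is screened will be considered as baseline and not reported as an AE". SAFTEE is absent from the screening list (7.2.2) and from the screening column of the Schedule of Events.
- Section 7.10.1 defines an adverse event as "any symptom, sign, illness or experience that develops or worsens in severity during the course of the study".
- For efficacy, Section 9 does specify change from baseline. Section 7.15 names change scores for AHRS and DESA in the DSMB report, but lists SAFTEE only as assessments.

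**The concern.** Safety and tolerability come first among the objectives in the Protocol Summary and form part of the primary objective (3.1). A contrast between two post-session ratings measures what a session caused only if the participant enters both sessions in the same state. With a one-week gap, someone who had PLIFUS first may enter the sham session still carrying an effect of PLIFUS. The post-sham rating then includes that effect, and the subtraction removes part of the signal the trial is meant to find. The loss falls on the longer-lasting effects.

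The contrast also picks up symptoms that vary from week to week for unrelated reasons. Anxiety, mood deterioration, neck pain and itching, all addendum items, can be present on a given day without any link to treatment. With 12 completers, that noise is not trivial.

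**Working it through.** The plan gives no safety effect size, event rate or precision figure, so there is none to reproduce. The check is two-period crossover algebra.

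**Inputs.** Twelve completers (Section 9); two sessions one week apart (4.1); random, counterbalanced order (Protocol Summary), with the exact split not stated. Assumed: b = stable symptom level, h = effect of PLIFUS, p = share of h still present at the next session, f = share given PLIFUS first.

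**1. Post-session values only, effect present at 1 hour.**
- PLIFUS first: (b + h) − (b + ph) = h(1 − p)
- Sham first: (b + h) − b = h
- Pooled: f·h(1 − p) + (1 − f)·h = h(1 − fp)

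| p | 4 of 12 PLIFUS first | 6 of 12 | 8 of 12 |
|---|---|---|---|
| 0 | 1.00h | 1.00h | 1.00h |
| 0.5 | 0.83h | 0.75h | 0.67h |
| 1 | 0.67h | 0.50h | 0.33h |

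For a binary symptom induced in 25% by PLIFUS and 0% by sham (assumed), with a 6:6 split and no background, the contrast is 0.25 × 0.75 = 0.188 at p = 0.5 and 0.25 × 0.50 = 0.125 at p = 1. The true value is 0.25.

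**2. Change from the same visit's pre-session rating.**
- PLIFUS first: [(b + h) − b] − [(b + ph) − (b + ph)] = h
- Sham first: [(b + h) − b] − [b − b] = h

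The pooled value is h for any p and f. A simulation at p = 1, 6:6 and h = 1 gave 0.51 for post-only and 1.01 for change.

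**3. Effect starting after the 1-hour rating and persisting in full, 6:6.**
- Post-only at 1 hour: 0 − h = −h if PLIFUS first and 0 if sham first, so −0.5h pooled. The effect appears to belong to sham.
- Change at 1 hour: 0 in both sequences, so it is missed.
- Post-only at 7 days: h − h = 0 if PLIFUS first and h − 0 = h if sham first, so 0.5h pooled.
- Change at 7 days: (h − 0) − (h − h) = h if PLIFUS first and (h − 0) − (0 − 0) = h if sham first, so h pooled.

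The later time points are therefore needed alongside the 1-hour one.

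**4. Background symptoms.** A symptom at the same level at both sessions cancels (b − b = 0). For prevalence q and between-session correlation r, the probability of being present at one named session only is q(1 − q)(1 − r). With q = 0.3 and r = 0.5 this is 0.105, or 12 × 0.105 = 1.26 participants in each direction. The expected net contribution is zero, and the SD of the mean difference is √(2 × 0.105/12) = 0.132. Over q = 0.1 to 0.5 and r = 0 to 0.8, the SD runs from 0.055 to 0.204.

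**5. Precision, with 25% induction, q = 0.3, r = 0.5, no persistence and background stable within a visit (all assumed).**
- Post-only: P(+1) = 0.105 + 0.595 × 0.25 = 0.254; P(−1) = 0.105 × 0.75 = 0.079. Mean 0.175; SD √[(0.3325 − 0.175²)/12] = 0.159.
- New onset at 1 hour: 0.7 × 0.25 = 0.175; SD √(0.175 × 0.825/12) = 0.110.
- One flag pooling onset at 1 hour, 1 day or 7 days (simulated): mean 0.150, SD 0.162.

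The 1-hour change has about half the variance of the post-only contrast (0.144 against 0.302 per person). Pooling the time points loses that gain and dilutes the contrast.

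**The case against.** The strongest reply is that safety here is descriptive and does not rest on one subtraction. Any symptom that develops or worsens is an adverse event, recorded with onset, severity, relationship and resolution (7.10.1, 7.11.2, 7.12). The DSMB sees unblinded safety data (7.15), and the halting rule (7.14) uses related events, not a SAFTEE difference. Neck pain starting an hour after PLIFUS would be on file whatever the contrast shows. All of this stands, and it limits the consequence. It does not repair the comparison: a descriptive difference is attenuated in the same way as a tested one, and no section says how adverse events are assigned to PLIFUS or sham when the conditions are compared.

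Second, persistence for a week may be rare. Section 2.2.2 cites mild, transient effects in 3.3% of 704 subjects. If p is near zero, so is the attenuation. That is fair, although the same section says PLIFUS has not been studied in schizophrenia.

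Third, the plan does not exclude the pre-session ratings. It is silent about their role in the contrast, and the Visit 2 rating evidently doubles as the one-week follow-up of session 1. This is correct, and it is why the dual role needs to be written down.

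**Conclusion.** The point holds as a correctable weakness in the safety comparison. The post-only contrast is attenuated by f × p: 25% at half persistence and 50% at full persistence under a 6:6 order, and 33% to 67% at full persistence if 4 to 8 of 12 receive PLIFUS first. Order split and persistence are assumptions. The precision gain at 1 hour also depends on the assumed background and induction rates.

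Four stronger readings are tempting, and the documents do not support them.
- A reader might infer that a lasting harm cancels to zero. That happens only within PLIFUS-first participants and only at full persistence; sham-first participants still show it, so the pooled value at 6:6 is halved.
- A reader might infer that symptoms already present are systematically charged to PLIFUS. Stable ones cancel, and fluctuating ones add noise without direction under random order.
- A reader might take screening as the SAFTEE baseline. Section 7.12 is an adverse event reporting rule, and SAFTEE is not given at screening.
- A reader might conclude that a lasting harm would go unseen. The adverse event record would still carry it to the DSMB.

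**What to change.** In 7.10, mirrored in Section 9, replace the post-versus-post comparison with the following:

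- Compare PLIFUS and sham on items that are new or worse than at the same visit's pre-session rating.
- Tabulate separately at 1 hour (SAFTEE and addendum), and at 1 day and 7 days (SAFTEE, addendum and C-SSRS), and show each table by sequence.
- State that the Visit 2 pre-session rating is both the 7-day reading for session 1 and the baseline for session 2.
- Do not combine the time points into a single emergent flag.
- Keep the raw post-session values as a listing.

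The cost is wording only, because every rating is already scheduled. There are two small downsides. An item already at maximum severity before a session cannot count as emergent, which is one reason to keep the listing. The 7-day table will still contain unrelated onsets: in a sham-first participant, anxiety starting on Day 5 for another reason would count as new after sham. MoCA, also a safety assessment (4.2.2), has no pre-session rating at the intervention visits, so this change does not extend to it.

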7.10.1 Definition of Adverse Events (AE)

An **adverse event** (AE) is any symptom, sign, illness or experience that develops or worsens in severity during the course of the study. Intercurrent illnesses or injuries should be regarded as adverse events. Abnormal results of diagnostic procedures are considered to be adverse events if the abnormality:

- results in study withdrawal
- is associated with a serious adverse event
- is associated with clinical signs or symptoms
- leads to additional treatment or to further diagnostic tests
- is considered by the investigator to be of clinical significance

7.10.2 Definition of Serious Adverse Events (SAE)

Serious Adverse Event

Adverse events are classified as serious or non-serious. A **serious adverse event** is any AE that is:

- fatal
- life-threatening
- requires or prolongs hospital stay
- results in persistent or significant disability or incapacity
- a congenital anomaly or birth defect
- an important medical event

Important medical events are those that may not be immediately life threatening, but are clearly of major clinical significance. They may jeopardize the subject, and may require intervention to prevent one of the other serious outcomes noted above. For example, drug overdose or abuse, a seizure that did not result in in-patient hospitalization, or intensive treatment of bronchospasm in an emergency department would typically be considered serious.

All adverse events that do not meet any of the criteria for serious should be regarded as **non-serious adverse events**.

7.10.3 Definition of Unanticipated Problems (UP)

Unanticipated Problems Involving Risk to Subjects or Others

Any incident, experience, or outcome that meets all of the following criteria:

- Unexpected in nature, severity, or frequency (i.e. not described in study-related documents such as the IRB-approved protocol or consent form, the investigators brochure, etc)
- Related or possibly related to participation in the research (i.e. possibly related means there is a reasonable possibility that the incident experience, or outcome may have been caused by the procedures involved in the research)
- Suggests that the research places subjects or others at greater risk of harm (including physical, psychological, economic, or social harm).

This definition could include an unanticipated adverse device effect, any serious adverse effect on health or safety or any life-threatening problem or death caused by, or associated with, a device, if that effect, problem, or death was not previously identified in nature, severity, or degree of incidence in the investigational plan or application (including a supplementary plan or application), or any other unanticipated serious problem associated with a device that relates to the rights, safety, or welfare of subjects (21 CFR 812.3(s)).

7.11 Classification of an Adverse Event

7.11.1 Severity of Event

For AEs not included in the protocol defined grading system, the following guidelines will be used to describe severity.

- **Mild** – Events require minimal or no treatment and do not interfere with the participant's daily activities.
- **Moderate** – Events result in a low level of inconvenience or concern with the therapeutic measures. Moderate events may cause some interference with functioning.
- **Severe** – Events interrupt a participant's usual daily activity and may require systemic drug therapy or other treatment. Severe events are usually potentially life-threatening or incapacitating.

7.11.2 Relationship to Study Agent

The research psychiatrist's assessment of an AE's relationship to sonication/sham is part of the documentation process, but it is not a factor in determining what is or is not reported in the study. If there is any doubt as to whether a clinical observation is an AE, the event should be reported. All AEs must have their relationship to study agent assessed. In a clinical trial, the study product must always be suspect. To help assess, the following guidelines are used.

- **Related** – The AE is known to occur with the study agent, there is a reasonable possibility that the study agent caused the AE, or there is a temporal relationship between the study agent and event. Reasonable possibility means that there is evidence to suggest a causal relationship between the study agent and the AE.
- **Not Related** – There is not a reasonable possibility that the administration of the study agent caused the event, there is no temporal relationship between the study agent and event onset, or an alternate etiology has been established.

For all collected AEs, the research psychiatrist who examines and evaluates the participant will determine the AE's causality based on temporal relationship and his/her/their clinical judgment. The degree of certainty about causality will be graded using the categories below.

- **Definitely Related** – There is clear evidence to suggest a causal relationship, and other possible contributing factors can be ruled out. The clinical event, including an abnormal laboratory test result, occurs in a plausible time relationship to drug administration and cannot be explained by concurrent disease or other drugs or chemicals. The response to withdrawal of the drug (dechallenge) should be clinically plausible. The event must be pharmacologically or phenomenologically definitive, with use of a satisfactory rechallenge procedure if necessary.
- **Probably Related** – There is evidence to suggest a causal relationship, and the influence of other factors is unlikely. The clinical event, including an abnormal laboratory test result, occurs within a reasonable time after administration of the drug, is unlikely to be attributed to concurrent disease or other drugs or chemicals, and follows a clinically reasonable response on withdrawal (dechallenge). Rechallenge information is not required to fulfill this definition.
- **Possibly Related** – There is some evidence to suggest a causal relationship (e.g., the event occurred within a reasonable time after administration of the trial medication). However, other factors may have contributed to the event (e.g., the participant's clinical condition, other concomitant events). Although an AE may rate only as "possibly related" soon after discovery, it can be flagged as requiring more information and later be upgraded to "probably related" or "definitely related," as appropriate.
- **Unlikely to be related** – A clinical event, including an abnormal laboratory test result, whose temporal relationship to drug administration makes a causal relationship improbable (e.g., the event did not occur within a reasonable time after administration of the trial medication) and in which other drugs or chemicals or underlying disease provides plausible explanations (e.g., the participant's clinical condition, other concomitant treatments).
- **Not Related** – The AE is completely independent of study drug administration, and/or evidence exists that the event is definitely related to another etiology. There must be an alternative, definitive etiology documented by the clinician.

